1.0 Project Summary/Abstract

Tissue ischemia (lack of blood flow) is one of the main causes of pressure injury. It is inevitable during bed-ridden condition or prolonged surgery procedure in the operating room. Previous studies demonstrated that the protective mechanisms of alternating pressure (AP) on pressure injury include redistribution of surface pressure, and allowing more blood supplies while lying on the support surface. The Dabir AP overlay is low profile yet possesses similar characteristics as other AP mattresses on the market. The objective of this study is to evaluate the protective mechanisms of Dabir AP overlay on weight bearing tissue of people with chronic spinal cord injury (SCI). Our central hypothesis is that the Dabir AP overlay will cause lower amount of interface pressure and allow more skin blood flow during weight bearing as compared to regular operation room (OR) overlay. In addition, people with SCI will have better tolerance to prolonged weight bearing after preconditioned with the Dabir AP overlay. This study will be repeated measures design, with subjects acting as their own control. Fifteen adults with chronic SCI will be recruited from the Greater Chicago area. Each subject will undergo two study protocols: lying on AP overlay followed by OR overlay (40 minutes each), and lying on OR overlay for 40 minutes only. Laser Doppler flowmetry system will be used to collect data before during and after lying on the overlays, and pressure mapping system will be used to measure interface pressure. Paired *t*-tests will be computed to compare the interface pressure and skin blood flow before, during and after lying on the overlays. Findings of this study will help determine the effectiveness of the Dabir AP overlay on pressure redistribution and ischemia preconditioning.

2.0 Background/Scientific Rationale

Tissue ischemia is one of the main etiologies of pressure injury.¹ It is inevitable during bed-ridden and wheelchair bound conditions, such as spinal cord injury (SCI), or prolonged surgery procedure in the operating room. Active alternating pressure (AP) mattresses are covered by Medicare policy for patients with multiple/large stage 2/ stage 3 pressure injuries to relief interface pressure and prevent recurrence of pressure injuries.² Previous studies demonstrated that the protective mechanisms of AP on pressure injury include redistribution of surface pressure, and allowing more blood supplies while lying on the support surface.³⁻⁵ The Dabir AP overlay (DabirAIR™, Dabir Surfaces Inc., Hardwood Heights, IL) is low profile yet possesses similar characteristics as other AP mattresses on the market; it is intended for clinical use, such as operation room (OR) where AP mattresses may not be an option. We expect Dabir AP overlay will be beneficial to people at risk of pressure injury by maintaining the blood supply during weight bearing condition.

In addition to pressure redistribution and increasing blood supplies, we also postulate that the if an AP overlay will be beneficial to the weight-bearing skin by means of preconditioning the skin with short-term ischemia, i.e. when air cells inflate. Ischemic preconditioning is a method used to prevent tissue damage caused by ischemic events, such as stroke and myocardial infarction,⁶ by means of slowing down ATP depletion in the short-term subsequent ischemic episodes and washing out the harmful catabolites during each short-term period of reperfusion. Recently, this method is implemented to heal diabetic foot ulcer by remotely precondition the lower limb.⁷ We hypothesize that the alternating pressure characteristics of the Dabir AP overlay could be utilized as a method for preconditioning to protect weight-bearing tissue in people with SCI.

To quantify the severity of tissue ischemia, we will collect the non-invasive reactive hyperemic response as an outcome. Reactive hyperemia is characterized by sudden increase in blood flow after temporary obstruction of the blood flow. Previous studies used this response to simulate the tissue response toward ischemia in people that are at risk of pressure ulcer, such as spinal cord injury.^{8,9}

People with SCI are at extremely high risk of pressure ulcer formation due to immobility and lack of sensation. In addition, this population may also have underlying change in vascular control mechanisms. To further quantify the vascular control mechanisms in our participants, we plan to use two additional protocols to provide objective measurements of blood supplies. The two non-invasive measurements are heat hyperemia and skin vasomotor response.

Heat hyperemia is an objective and non-invasive method to quantify the degree of impaired thermoregulation. It is characterized by a biphasic pattern with an initial peak (initiated by activity of sensory nerves and modulated by sympathetic nerves), followed by a brief nadir and a plateau phase (mediated by local production of endothelial nitric oxide).⁸ A previous study showed that the initial peak was diminished significantly at skin sites below level of injury in patients with complete SCI.⁹ Given that increased skin temperature is a well-proven risk factor in ulcer formation in addition to prolonged pressure,¹⁰ adopting measurement of thermoregulatory function may assist in understanding the pathological patterns related to ulcer formation.

Skin vasomotor response is a reduction in SBF induced by standardized cutaneous electrical stimulation. It is an objective method to assess the integrity of sympathetic pathways,¹¹ and it is a sensitive tool in identifying sympathetic function below a spinal cord lesion.¹² Measurement of the skin vasomotor response may provide us a comprehensive understanding of the changes in control mechanisms with the pathological pattern in SBF detected before ulcer formation.

By comparing the skin blood flow responses between using Dabir AP overlay vs. standard OR overlay, we might be able to fill the gap of current research by determining the potential benefit of Dabir AP overlay on pressure ulcer prevention.

3.0 Objectives/Aims

The objective of this study is to evaluate the protective mechanisms of Dabir AP overlay on weight bearing tissue of people with chronic spinal cord injury (SCI). Our central hypothesis is that the Dabir AP overlay will cause lower amount of interface pressure and allow more skin blood flow during weight bearing as compared to regular OR overlay. In addition, people with SCI will have better tolerance to prolonged weight bearing after preconditioned with the Dabir AP overlay.

There are three aims (with related hypotheses) for this study:

Aim 1: To determine the effectiveness of pressure redistribution with Dabir AP overlay.

Hypothesis 1. Our participants will demonstrate lower interface pressure at sacrum and heel when lying supine for 40 minutes on Dabir AP overlay as compared to that on regular OR overlay (AliMed®).

Aim 2: To examine the severity of tissue ischemia with the use of Dabir AP overlay.

Hypothesis 2a. Our participants will demonstrate greater skin blood flow at sacrum and heel when lying supine for 40 minutes on Dabir AP overlay as compared to that on regular OR overlay.

Hypothesis 1b. Our participants will demonstrate smaller reactive hyperemic response at sacrum and heel after being relieved from 40 minutes of lying supine on Dabir AP overlay as compared to that on regular OR overlay.

Aim 3: To assess the feasibility of utilizing Dabir AP overlay for ischemic preconditioning for prolonged weight bearing condition.

Hypothesis 3. With 40 minutes of preconditioning using the Dabir AP overlay, our participants will demonstrate smaller reactive hyperemic response at sacrum and heel after being relieved from the regular OR overlay as compared to that without preconditioning.

4.0 Eligibility

Twenty people with chronic SCI will be recruited from the Greater Chicago area. The eligibility of the subjects will be determined by the study team based on the following criteria.

4.1 Inclusion Criteria

- Males and females 18-64 years old
- have had spinal cord injury for more than one year
- have injury level at T10 or above
- not ambulatory and use a wheelchair for mobility
- non smokers or able to refrain from smoking four hours prior to and during the study

4.2 Exclusion Criteria

- current pressure ulcer
- history of diabetes mellitus
- history of cardiovascular diseases
- history of hypertension
- history of pulmonary diseases
- pregnant women (based on screening and pregnancy testing)
- non-English speakers

4.3 Excluded or Vulnerable Populations

No vulnerable population will be included in the study. Since all key investigators are fluent only in English language, non-English speaking subjects will not be included.

5.0 Subject Enrollment

Subjects will be eligible to participate in this study if they meet the study criteria as determined by the telephone screening and face-to-face screening procedures.

Telephone Screening Procedure (approximately 15 minutes)

Subjects will be recruited from the Greater Chicago area through study flyers. The PI or key personnel will recruit the eligible subjects when potential subjects call in response to the flyer. Questions regarding the inclusion and exclusion criteria will be asked to determine the eligibility based on the telephone screening script. Results of the telephone screening will be documented in Forms A, B, C1, C2, and D. If the potential subject is not eligible, results and confidential information will be destroyed immediately. All potential subjects will be scheduled to a study visit at the UIC Applied Health Sciences Building room 272 for further screening. Subjects will be asked to fast and refrain from smoking four hours prior to and during the study, and refrain from consuming any caffeinated foods/drinks for 12 hours prior to the study.

Face-to-face Screening Procedure (approximately 30 minutes)

Upon arrival for the study visit, the PI or key personnel will inform the potential subject of the study procedures and risks and benefits of the study. A consent form with details of all procedures, risks and benefits will be provided to the potential subject. Once the PI or key personnel receive the signed consent form, the subject will proceed to face-to-face screening. During the face-to-face screening procedure, the PI or key personnel will measure the resting heart rate and blood pressure with heart rate monitor and blood pressure cuff respectively and documented in form E1. The PI or key personnel will also examine the remaining motor function, sensation and autonomic function after spinal cord injury. The remaining sensation, motor, and autonomic function are standard physical examination for people with SCI in the clinic. The remaining sensation will be tested with the key personnel performing light touch of the skin below the level of injury (as the picture shown in form E2), and the motor function will be tested with the key personnel instructing subject to perform joint movement below the level of injury. Results of the remaining sensation and motor function will be documented in form E2. The autonomic function will be tested by asking subject questions regarding their ability to sweat, ability to sense the changes in temperature, bladder function, bowel movement and sexual function, and results will be documented in form E3. If the subject demonstrates normal heart rate and blood pressure, the subject will proceed with the study procedures. Women of childbearing age will also be screened for pregnancy using a urine pregnancy test strip. Women who are pregnant will not be eligible to participate.

6.0 Study Design and Procedures

Study Design. This study uses a repeated measures design, and each subject will act as his/her own control. Each subject will undergo the two protocols in the experimental procedures: AP protocol and Control protocol. To ensure the order of the two protocols are randomized, the order of AP and Control protocols will be determined by drawing one envelope from the envelope pool. We will start with a pool of total 20 envelopes (10 envelopes indicating AP protocol first, and 10 envelopes indicating control protocol first). Once the envelope is drawn from the pool, it will not return to the pool.

Study Procedures (Research purpose). After enrollment, subjects will proceed to the following procedures: 1) experimental procedures, 2) vascular control measures, 3) pressure mapping of wheelchair and 4) blood withdraw.

1) **Experimental procedure (approximately 4.5 hours)**

Each subject will undergo two study protocols: AP and control (figure 1), and the order of the protocols will be randomized as described previously. A 30-minute washout period will be provided in between the two protocols. Two Laser Doppler flowmetry (LDF) flat probes (moor instrument, Wilmington, DE) will be taped to the sacrum and one heel to collect the skin blood flow response throughout both AP and control protocols. A whole body pressure mapping system (Xsensor, Xsensor Technology Corp., Alberta, Canada) will be used between the subject and the overlay to collect the inter pressure data. For the AP cycle, we will use four 10-minute cycles (5 minutes of high pressure and 5 minutes of low pressure).

AP protocol: The subject will first lie on his/her side quietly for 10 minutes to collect the baseline skin blood flow, followed by lying supine on the Dabir AP overlay for 40 minutes, and then side lying for 30 minutes to collect the first reactive hyperemic response. To test the effect of preconditioning, the subject will then lie supine on the OR overlay for 40 minutes followed by side lying for 30 minutes for the second reactive hyperemic response.

Control protocol: The subject will first lie on his/her side quietly for 10 minutes to collect the baseline skin blood flow, followed by lying supine on the OR overlay (AliMed®) for 40 minutes, and then side lying for 30 minutes to collect the reactive hyperemic response for control protocol.

AP	Baseline (10 min)	AP overlay (40 min)	RH 1 (30 min)	OR overlay (40 min)	RH 2 (30 min)
Ctrl	Baseline (10 min)	OR overlay (40 min)	RH (30 min)		

Figure 1. Illustration of the full course of the experimental protocols: Alternating pressure (AP, top panel) and Control (Ctrl, bottom panel).

2) Vascular control measures (approximately 30 minutes)

The PI, or key personnel will then collect the vascular control measures, including the heat hyperemic (HH) blood flow response, and the skin vasomotor response. A non-invasive combined laser Doppler and white light reflectance spectroscopy (LDF-WLRS) probe (CP2T-1000, Moor Instrument, Wilmington, DE) will be used for both measures.

HH blood flow response will be measured at the sacrum and one heel while the subject is in side-lying position. Figure 2 demonstrates the HH measurement setting. HH will be induced with the heater at the tip of the probe head (41°C for 5 minutes). This HH measure will take approximately 7 minutes (2 min-baseline, 5 min-heating) per location. In total, the HH measures will take up to 15 minutes to complete.

The skin vasomotor response will be induced using cutaneous electrical stimulation (3-10 mA, 0.2-1.0 ms pulses at 20 Hz, 1 s trains) delivered via 1 cm Ag-AgCl surface electrodes applied bilaterally (4 cm apart) to the forehead (above lesion) and the abdominal wall (below lesion) while the subject is in a semi-reclined position.¹² For each site, 5-8 stimuli will be delivered randomly. CP2T-1000 probe will be used to collect SBF and tissue oxygenation data at pulp of the second finger and toe. Subject will be in a semi-reclined position (about 30° from horizontal plane) during this protocol, and it will take up to 15 minutes to complete this protocol.

[figure not shown]

Figure 2. (A) hand held LDF-WLRS probe with heater ring, (B) HH measure.

3) Pressure mapping of wheelchair (approximately 10 minutes)

The subject will be asked to transfer back to his/her wheelchair with the pressure mapping system placed between the wheelchair and the subject to collect the interface pressure data. The pressure mapping system is the same as that used between the subject and overlay to collect the interface pressure data.

4) Blood withdraw (approximately 15 minutes)

The key personnel will draw venous blood samples (total 20 mL) via venipuncture for standard blood tests, including glycated hemoglobin (HbA1C), plasma glucose, lipid and lipoprotein concentrations (i.e. total-cholesterol, low-density lipoprotein, triglycerides, and high-density lipoprotein). The rationale for making these measurements is to collect potential covariates that might affect skin blood flow responses. Blood samples not used to probe for blood sugar and lipid profile tests will be stored up to five years (or until exhausted) for further analyses, since latest trend in literatures demonstrated metabolic syndrome after spinal cord injury had an effect on pressure ulcer formation.¹³

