12.0 Statistical Considerations

For aims 1 and 2, paired *t*-tests will be computed to compare the interface pressure and skin blood flow during 40 minutes of AP overlay (AP protocol) vs. OR overlay (Ctrl protocol). Paired *t*-tests will also be used to compare the reactive hyperemic response during RH1 (AP protocol) vs. RH (Ctrl protocol). For aim 3, paired *t*-tests will be computed to compare the skin blood flow during OR overlay (AP protocol) vs. OR overlay (Ctrl protocol), and the reactive hyperemic response during RH2 (AP protocol) vs. RH (Ctrl protocol). SPSS will be used for all statistical analyses. Since this is a pilot study, we will test the study on 15 subjects. Results from this study will be used to calculate sample size for future studies. In case of dropout or subject decease during this study, we propose to recruit up to 20 subjects for this study.

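### Order comes from one block of 20 envelopes but the plan tests 15 subjects, leaving a 30.3% chance of a 9:6 or 10:5 order split; minor, and nearly free to fix

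*Combined protocol and SAP*

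**What the plan says.** Section 6.0 describes a single pool: "We will start with a pool of total 20 envelopes (10 envelopes indicating AP protocol first, and 10 envelopes indicating control protocol first". It adds: "Once the envelope is drawn from the pool, it will not return to the pool". No smaller sets within the pool are described.

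Three places give the number of subjects:
- Section 1.0: "Fifteen adults with chronic SCI will be recruited from the Greater Chicago area".
- Section 4.0: "Twenty people with chronic SCI will be recruited from the Greater Chicago area".
- Section 12.0: "Since this is a pilot study, we will test the study on 15 subjects", followed by "In case of dropout or subject decease during this study, we propose to recruit up to 20 subjects for this study". No dropout rate is given.

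Both protocols belong to one experimental procedure of about 4.5 hours. Section 6.0 says: "A 30-minute washout period will be provided in between the two protocols". The AP protocol has two loadings, because after the AP overlay and the first recovery "the subject will then lie supine on the OR overlay for 40 minutes". The control protocol has one loading.

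Section 12.0 compares AP-protocol and control-protocol measurements by paired t-tests for all three aims. It mentions no period, sequence or carryover term.

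**The concern.** The pool is sized for 20 draws, but the analysis is planned on 15. Stopping a block of 20 at 15 leaves the order split to chance.

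Order could matter in this layout. The two protocols follow each other in one session, and the control loading is either the first or the third of three loadings. Hypothesis 3 itself proposes that AP exposure changes the response to a later load on the OR overlay. In AP-first subjects the control load is such a later load.

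In an unadjusted paired difference, a shift between the first and second protocol cancels only as far as the two orders are balanced. The split also decides how many of the 15 control loads in the Aim 3 comparison follow AP exposure: anywhere from 5 to 10. Section 12.0 says the results will feed the sample size of future studies, so an accidental order mix would carry into that calculation.

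**Working it through.** The plan states no figure for order balance and no power calculation, so there is nothing to reproduce.

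**Inputs.** Pool of 10 AP-first and 10 control-first envelopes, drawn without replacement (section 6.0). 15 subjects (sections 1.0 and 12.0). 20 as the number recruited (section 4.0) or as the upper limit (section 12.0).

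**1. Split after 15 draws.** Let X be the number of AP-first envelopes. Then P(X = k) = C(10,k) × C(10,15−k) / C(20,15), with C(20,15) = 15,504.

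| Split, either direction | Number of draws | Probability |
|---|---|---|
| 8:7 | 2 × 45 × 120 = 10,800 | 69.7% |
| 9:6 | 2 × 10 × 210 = 4,200 | 27.1% |
| 10:5 | 2 × 1 × 252 = 504 | 3.3% |

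9:6 or worse: (4,200 + 504) / 15,504 = 30.3%.

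**2. Dropout.** If all 20 envelopes are drawn and 15 subjects complete, with dropout unrelated to order, the completers are a random 15 from 10 + 10. The formula is the same, and so is the 30.3%.

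**3. Other numbers drawn and analysed.** The chance that the orders differ by three or more is 8.7% at 16, 21.1% at 17, and 0% at 18, 19 and 20. At 20 the split is exactly 10:10.

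**4. Effect on the unadjusted paired difference.** Let δ be the true AP-minus-control difference and π an additive shift of the second protocol relative to the first. An AP-first subject contributes δ − π and a control-first subject δ + π. With nA AP-first and nC control-first subjects, the mean is δ + π(nC − nA)/15. The share of π left in, ignoring sign, is:
- 8:7: 1/15 = 6.7%
- 9:6: 3/15 = 20%
- 10:5: 5/15 = 33%

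Averaged over the draw: 0.697 × 6.7% + 0.271 × 20% + 0.033 × 33.3% ≈ 11%. The lowest possible value with 15 subjects is 6.7%.

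**5. Effect on an order-adjusted estimate.** Its variance is proportional to 15²/(4·nA·nC): 225/224 at 8:7, 225/216 at 9:6 and 225/200 at 10:5. Relative to 8:7 this is 224/216 = +3.7% and 224/200 = +12.0%.

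**6. Sets of four.** Three complete sets give 6:6 after 12 subjects. The next three draws come from a 2 + 2 set and must fall 2:1, so the split after 15 is always 8:7. Five sets give 10:10 after 20.

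**7. What balance cannot repair.** In AP-first subjects the AP, second OR and control loads are loadings 1, 2 and 3. In control-first subjects the control, AP and second OR loads are loadings 1, 2 and 3. At an even split, the mean position of the AP-overlay load minus the control load is (−2 + 1)/2 = −0.5 loading for Aims 1 and 2. For Aim 3, the second OR load minus the control load is (−1 + 2)/2 = +0.5. If the response drifted linearly with each loading, half a loading of drift would remain in each contrast even with perfect balance.

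**The case against.** The case for leaving the scheme alone has several sound parts.

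- **The pool is already a block.** A reader might infer that the order is randomized without any blocking. The documents do not support that: 10 + 10 without replacement is one block of 20. It caps the imbalance at 10:5, and a fair coin for each of 15 subjects would give 9:6 or worse 60.7% of the time. If the twenty in section 4.0 is the number drawn and analysed, the split is exactly 10:10. This stands, and it ties the 30.3% to 15 subjects.
- **Imbalance is not harm.** A reader might take 30.3% as the chance of a biased result. The documents give no size for any period or carryover effect. Order is still random, so the imbalance has no preferred direction. The average residual share falls only from about 11% to 6.7%. This stands too.
- **Smaller sets do not make the comparison clean.** A reader might infer that balanced orders would make the pooled t-tests sound. Carryover across the 30-minute gap and the first-or-third position of the control load remain. With sets of four, 7 or 8 of the 15 control loads still follow AP exposure, and the present scheme averages 7.5.
- **Dropout undoes the guarantee.** If 20 are drawn and 15 complete at random, both schemes start at 10:10 and give the same 30.3% among completers.

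The objection does not remove the mismatch itself. Two sections plan 15 subjects, the pool is balanced only at 20, and section 12.0 states nothing that would absorb an uneven split.

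**Conclusion.** The point holds and is minor. The 30.3% is exact for 15 subjects drawn. It also applies to 15 completers out of 20 if dropout is unrelated to order. It does not apply if 18 or more are drawn and analysed. The consequence, 20% or 33% of a first-versus-second effect left in the mean difference instead of 6.7%, assumes that the effect is additive and that the t-tests are run without an order term, as section 12.0 reads. That order matters at all is inferred from the layout and from Hypothesis 3; the documents do not measure it. The missing order term in section 12.0 is the weightier weakness. The envelope scheme merits a change mainly because the change costs almost nothing.

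**What to change.** In section 6.0, divide the same 20 envelopes into five sealed sets of four, each with two AP-first and two control-first, and use up one set before opening the next. State one consistent number to be recruited, drawn and analysed in sections 1.0, 4.0 and 12.0. Add an order (period) term or a by-order summary to section 12.0 alongside this change.

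The cost is re-sorting the envelopes and a few changed sentences, best done before the first draw. No subject, visit or procedure is added. The downside is some predictability. The last order in a set can always be worked out. The last two can be worked out when the first two match, which happens in 2 of the 6 possible arrangements, or one third of sets. The harm is limited because every subject receives both protocols. The 8:7 guarantee covers subjects drawn, so the split among completers should be reported.

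### Section 12 pools both protocol orders and makes no use of the randomized order, although in AP-first subjects the Aim 3 control load is the third load of the same session

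*Combined protocol and SAP*

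**What the plan says.** Section 6.0 places both protocols under one item, "Experimental procedure (approximately 4.5 hours"), and says "A 30-minute washout period will be provided in between the two protocols". The order is drawn from 20 envelopes, 10 for each order, without replacement. Form F records which order was used.

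The AP protocol contains two loads. After the AP overlay and the first recovery period, "To test the effect of preconditioning, the subject will then lie supine on the OR overlay for 40 minutes". The control protocol contains one OR-overlay load.

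Hypothesis 3 (section 3.0) concerns the hyperemic response "after being relieved from the regular OR overlay as compared to that without preconditioning". For this aim, section 12.0 plans paired t-tests of two kinds. One is to "compare the skin blood flow during OR overlay (AP protocol) vs. OR overlay (Ctrl protocol"). The other takes recovery after loading as its outcome: "the reactive hyperemic response during RH2 (AP protocol) vs. RH (Ctrl protocol"). Aims 1 and 2 also use paired t-tests against the control run, for interface pressure, skin blood flow and RH1. Neither section 9.0 nor section 12.0 mentions order, period, carryover or a by-order summary. Section 12.0 adds: "Results from this study will be used to calculate sample size for future studies".

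**The concern.** Aim 3 needs a control load that has not been preconditioned. In subjects who draw AP first, the control load follows the AP overlay in the same session, at the same sacrum and heel.

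Aim 3 itself supposes that the AP effect survives the 30-minute RH1 rest before the next load. The washout is also 30 minutes, and the documents give no basis for it and no duration for the effect. The rationale in section 2.0, "slowing down ATP depletion in the short-term subsequent ischemic episodes", fits a short-lived effect as well as a lasting one.

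If some effect persisted, the pooled Aim 3 difference would be diluted. Cumulative loading or drift over the session could move it either way. Section 12 has nothing that would reveal or qualify this, and the results are meant to size later studies.

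**Working it through.** **Session length.** AP protocol 10 + 40 + 30 + 40 + 30 = 150 min; washout 30 min; control protocol 10 + 40 + 30 = 80 min. The total is 260 min = 4.33 h, which agrees with the stated 4.5 h. Without a separate washout it would be 230 min = 3.83 h.

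**Load starts, in minutes from session start.**

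| | AP-first | Control-first | Mean at an even split |
|---|---|---|---|
| AP overlay | 10 (load 1) | 120 (load 2) | |
| OR overlay, AP protocol | 80 (load 2) | 190 (load 3) | |
| OR overlay, control | 190 (load 3) | 10 (load 1) | |
| RH2 load minus control load | −110 min, −1 load | +180 min, +2 loads | +35 min, +0.5 load |
| RH1 load minus control load | −180 min, −2 loads | +110 min, +1 load | −35 min, −0.5 load |

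In AP-first subjects AP ends at 50 and the control load starts at 190, a gap of 140 min. In control-first subjects the control load ends at 50 and AP starts at 120, a gap of 70 min. Because the AP protocol has two loads and the control has one, randomizing the order does not balance load position, even at a perfect split.

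**How uneven the draw can be.** For 15 envelopes drawn from 10 + 10 (hypergeometric), the probabilities of 5, 6, 7, 8, 9 and 10 AP-first are 0.016, 0.135, 0.348, 0.348, 0.135 and 0.016. So 7:8 either way has about 70%, 6:9 or more uneven about 30%, and 5:10 either way 3.3%. With a share p AP-first, the mean RH2 position gap is −110p + 180(1 − p): +64 min at 6/15, +6 at 9/15, and at the extremes +83 at 5/15 and −13 at 10/15. Weighting the two orders equally holds it at +35.

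**Dilution, under assumption.** Let f be the fraction of the Aim 3 effect still present in the control run of AP-first subjects, with no other order effect. The AP-first mean difference is then (1 − f) of the truth and the control-first difference is the full truth, so the pooled estimate is 1 − fp.
- At p = 1/2: 100%, 87.5%, 75% and 50% for f = 0, 0.25, 0.5 and 1. The last means no decay at all.
- At f = 0.5: 83% with 5 AP-first and 67% with 10. Equal weighting holds it at 75%.

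**Precision, 95% half-widths in SD of the difference, n = 15.**
- Pooled: t(14)/√15 = 0.554.
- Order-adjusted: t(13) × ½ × √(1/n₁ + 1/n₂) = 0.559 at 7:8, 0.569 at 6:9 and 0.592 at 5:10.
- By order: 0.84 at n = 8 and 0.92 at n = 7.

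**Could the trial detect carryover?** Assume a true effect of 0.78 SD (80% power for the paired test at n = 15) and a within-subject correlation of 0.5. A 7-versus-8 comparison of control RH between orders would reach two-sided 0.05 in about 6%, 11% and 29% of trials at f = 0.25, 0.5 and 1.

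**The case against.** - **Carryover is not demonstrated.** The relevant gap is 140 minutes rather than 30, and the control run has its own fresh baseline. This stands. A reader might infer from the 30-minute washout that the Aim 3 control is contaminated. The documents do not support that, because they give no duration for the effect.
- **The order is randomized.** This balances which protocol comes first. It balances neither load position nor AP carryover into the control run.
- **The uneven-draw argument is limited.** Section 4.0 speaks of twenty recruits. If all 20 envelopes are used and all subjects complete, the split is 10:10 and the order-adjusted point estimate equals the pooled one. This stands. Taking the error term within order would still remove order variation from the interval.
- **Order adjustment does not remove carryover.** Correct: equal weighting leaves the factor at 1 − f/2 and the position gap at +35 minutes. The by-order results do not isolate carryover either, since the control-first group, whose control is free of AP carryover, has the largest offset (+180 minutes, +2 loads).
- **A first-protocol-only comparison might seem the clean answer for Aim 3.** It is not. It sets load 2 at minute 80 against load 1 at minute 10, a gap of +70 minutes and +1 load, twice the pooled imbalance.
- **One session is inferred.** Section 8.0 numbers a visit and Form F has a session column, which could hint at more than one visit. A 30-minute washout inside a 4.5-hour procedure outweighs both.
- **This is a pilot without a power claim.** True, and it limits the seriousness. The stated use for later sample sizes is why the caveat should still be written down.

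**Conclusion.** The point holds as a gap in the analysis and reporting plan. Order is randomized and recorded but not used, and the Aim 3 control occupies different positions in the two orders: first load, or third load 140 minutes after AP. From the documents alone, the RH2 load starts on average 35 minutes and half a load later than its control at an even split. If 15 envelopes are drawn, 30% of draws are 6:9 or more uneven.

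The dilution of 1 − f/2 rests on an assumed f, which could be zero. A reader might go further and conclude that Aim 3 is biased toward no effect, or that a later trial would be oversized by a known factor. Neither follows: prior loading or time in session could act in the opposite direction, and this trial can neither confirm nor exclude carryover. The change would keep the Aim 3 conclusion within what the data support; it would not diagnose carryover.

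**What to change.** In section 12:

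1. For each contrast of the AP protocol with the control run (interface pressure, skin blood flow during the AP overlay, RH1, skin blood flow during the AP-protocol OR overlay, RH2), keep the paired t-test. Add an order-adjusted estimate with 95% CI: the equally weighted mean of the two order-specific mean differences, with the error term taken within order. Say that it guards against an uneven draw and order variation and does not remove carryover.
2. For the two Aim 3 contrasts, report the paired differences by order with 95% CIs, descriptively and without a carryover test.
3. State, whether the result is null or positive, that the Aim 3 estimate may be affected by carryover, prior loading or time in session and that this trial cannot separate them. Carry the caveat into any future sample-size calculation.
4. Do not use a first-protocol-only comparison for Aim 3. It may be kept as an optional sensitivity estimate for RH1 versus RH and for blood flow on the AP versus control OR overlay, where both are load 1 at minute 10. Its half-width is about 1.12 SD at 7 versus 8 (assumed correlation 0.5, before baseline adjustment).

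In section 6, state that the sufficiency of the 30-minute washout is an assumption.

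The cost is wording and extra output from data already collected; no procedure changes. With three hyperemia parameters (section 9.0), two sites, and one summary per site for blood flow and for pressure, item 1 adds 2 × 3 × 2 + 2 × 2 + 2 = 18 intervals. Item 2 adds (3 × 2 + 2) × 2 = 16. The by-order intervals will be wide and should qualify the pooled result, not replace it.
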